6.2.4. Derived and Transformed Data

6.2.4.1. Primary Efficacy Variables

The co-primary efficacy endpoint is functional independent sitting at the 18 months of age visit.

Functional independent sitting: this is assessed by video evaluation by an expert reviewer of videos taken either at scheduled visits (see

Table 4 and

Table 5) or provided by parent/legal guardian, if patient meets the criterion:

- Child sits alone without support for at least 30 seconds. This will be collected from external dataset.

The other co-primary endpoint, event-free survival, is defined as avoidance of any one of the following events up to 14 months of age, whichever occurred first:

- Death, *or*
- Tracheostomy, *or*
- Noninvasive Ventilatory support \geq 16-hour per day *and* continuously \geq 14 days

Usage data for patients using non-invasive ventilatory support will be extracted directly from the device (Triology 100, Trilogy 200) on an SD card, and transferred as an external dataset. Average daily use of non-invasive ventilatory support by visits (if available) will be calculated. If a patient did not have a Trilogy device at baseline and was using non-invasive ventilatory support prior to screening, the average daily usage will be based on parent report and documented in the source documentation. As a secondary analysis, the amount of ventilation support will be categorized into None, >0 - \leq 12 hours, >12 - $<$ 16 hours, \geq 16 or permanent ventilation. The count and percent of patients in each ventilation support category at each visit (if available) will be displayed.

6.2.4.2. Supportive (Secondary) Efficacy Variables

Supportive (secondary) efficacy variables are as follows:

- Proportion of patients who did not require parenteral nutrition prior to therapy who maintain the ability to thrive, defined by the ability to tolerate thin liquids as demonstrated through a formal swallowing test, do not receive nutrition through mechanical support (i.e., feeding tube), and maintain weight (>third percentile for age and gender) at 18 months of age.
- Proportion of patients who are independent of ventilatory support, defined as requiring no daily ventilator support/usage at 18 months of age, in the absence of acute reversible illness and excluding perioperative ventilation.

6.2.4.3. First observed date of video confirmed milestone

Home recorded milestone video will be brought by parents at the official clinical visit, which will be assessed by investigator at the site. If the investigator confirms the milestone, the recording will be captured in [REDACTED] and the video will be uploaded for central review. If the central reviewer confirms the milestone, the first observed date will be the date captured in [REDACTED]. If the central reviewer is not able to confirm the milestone, the attempt will be made

to confirm the milestone in the next clinical visit. If confirmed in the next clinical visit, the reported first observed date of the confirmed milestone will be the end date of that clinical visit. This alternative process is due to clinical operation difficult.

6.2.4.4. Safety Variables

The safety endpoint is defined as the patient meeting the following criteria:

- Unanticipated toxicity event of Grade ≥ 3 (as per CTCAE)
- Adverse events of special interest (see Section 10.3.2.4)
- ‘Possibly Related’ or ‘Probably Related’ or ‘Definitely Related’ to study treatment
- Requires medical treatment or presents with symptoms

This will be collected at all scheduled visits (see [Table 1](#)) from patient’s CRF. Adverse Event collection methods for the observational natural history cohort were not consistent with rigorous Adverse Event collection methods demonstrated in the context of an interventional clinical research study; therefore, only descriptive statistics will be presented.

6.3. Handling Missing Data

All patients in the ITT analysis set will be included in the primary efficacy analysis for a given endpoint provided there are non-missing baseline values. If a patient misses a regularly scheduled visit, every attempt will be made to reschedule a visit within that visit window to obtain evaluations or tests.

[figure not shown]
For co-primary and co-secondary endpoints, missing values will be imputed as non-responsive.

Additional sensitivity analyses will be performed if there is at least 1 missing value. They include:

- An analysis based on completer population, from which the missing value(s) will be excluded.
- An estimate based on missing values imputed as follows:
 - Set the value to nonresponsive, if a patient discontinues the study due to an AE or experiences death for missing data occurring after these events.
 - Set the value based on the last available response, if otherwise.
- An estimate based on multiple imputation may be carried out using last available response, assuming Missing at Random (MAR).

If an endpoint value is a composite “response-type” (such as maintain ability to thrive) at any visit which is missing due to missing values in any of the components, while the patient is still enrolled (this is expected to happen very infrequently), it may still be possible to determine the response status using those component variables that are not missing. In this case, no imputation method is needed. However, if the response status cannot be determined in the presence of missing components, the method of last observation carried forward (LOCF) or non-responsive will be specified explicitly when applied to any of the missing

components. From that mix of actual and carried-forward values, the value of the “response-type” endpoint at 18 months of age will be determined. This type of LOCF method will be known as “LOCF mixed components,” since it is based on calculating the composite value based on a mixture of values at a visit and values carried forward from previous visits.

For the CHOP-INTEND and BAYLEY instruments, rules suggested by the producers of these assessments will be followed in calculating scores when individual question/items may be missing. If these rules are not enough for calculating a score, then the endpoint will be considered as having a missing value, and this missing value may be addressed as specified in the two paragraphs above or left as missing if acceptable.

Missing values in any of the endpoints will not be imputed when summarizing these endpoints using descriptive statistics.

In addition, missing values for safety endpoints will not be imputed.

Table 2: Rules of Date Imputation: Pre-Dose Data

Partial Missing Start or Stop Date	Imputed Start Date	Imputed Stop Date
Missing month and day, but the year is present	January 1 of that year or dose date if the year is the same as the year of dose date	December 31 of that year
Missing day, but year and month are present	First day of that month or dose date if the year and month are the same as the year and month of dose date	Last day of that month
Missing month, but year and day are present	Missing month imputed as January	Missing month imputed as December

Table 3: Rules of Date Imputation: Post-Dose Data

Partial Missing Start or Stop Date	Imputed Start Date	Imputed Stop Date
Missing month and day, but the year is present	Date of dose	December 31 of that year

Partial Missing Start or Stop Date	Imputed Start Date	Imputed Stop Date
Missing day, but year and month are present	First day of that month or dose date if the year and month are the same as the year and month of dose date	Last day of that month
Missing month, but year and day are present	Date of dose	Missing month imputed as December

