5.2. Intent-to-Treat (ITT) Population

The ITT population will consist of symptomatic patients with bi-allelic deletion of *SMN1* (exon 7/8 common homozygous deletions) and 2 copies of *SMN2* without the known gene modifier mutation (c.859G>C) who receive an IV infusion of AVXS-101 at less than 180 days of age. The first three patients enrolled must meet the criteria for the Intent-to-Treat Population.

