8. EFFICACY

8.1. Primary Efficacy Endpoints and Analysis

8.1.1. Co-Primary Efficacy Endpoint: Functional Independent Sitting at 18 months of age

An independent expert reviewer will evaluate recorded videos of CHOP-INTEND or Bayley Scales assessments conducted at clinic visits. The reviewer will judge whether the video reveals evidence of the milestone achievement of functional independent sitting [REDACTED].

During the Screening visit, the physical therapist will complete an assessment of baseline milestone achievement, including functional independent sitting; this assessment must address all milestones/items noted in [Appendix 21.1](#) that are at or below the child's expected function for age. Items that are below the child's expected function for age that are not successfully achieved during the baseline evaluation should be repeated at subsequent visits until successfully performed.

The milestones of sitting independently (Bayley Scales gross motor subtests item 22 and 26) will be assessed at every subsequent visit regardless of starting point on the scale. These milestones will also be assessed at the 18 months of age visit, regardless of previous attainment, as the Bayley Scales do not necessarily require the child to repeat previously attained milestones.

The number and percent of patients whom, through video evidence, exhibit the milestone achievement of independent sitting for at least 30 seconds at 18 months of age study visit will be summarized for the ITT population. Potential missing values will be imputed per [Section 6.3](#). A one-sided Exact Binomial Test will be used to test the null hypothesis of $p=0.1\%$ at significance level of 0.025. Furthermore, the corresponding 97.5% confidence intervals will be estimated by the exact method for binomial proportions.

In case for the presence of missing value, sensitivity analyses outlined in [Section 6.3](#) will be carried out to evaluate the appropriateness of assumptions for the missing data.

Additionally, for patients who achieve the functional independent sitting at 18 months of age visit, the age at which the subjects first achieved independent sitting for 30 seconds will be summarized.

8.1.2. Co-Primary Efficacy Endpoint: Avoidance of Death or Surrogate for Death (Permanent Ventilation)

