For a participant who develops an acute reversible illness and/or requires perioperative ventilator support, a recovery period not to exceed 21 days following the date of definitive intervention will be instituted. Following this recovery period, the condition will be considered sub-acute and the participant will become evaluable with regards to the surrogate survival endpoint (Requirement of ventilator support of ≥ 16 hours/day for greater than 14 days).

Example: Using this approach it would mean that on day 1, patient A receives definitive intervention for an acute reversible illness resulting in ventilator support for ≥ 16 hours/day. Days 1-21 will be provided to permit recovery from the acute reversible illness. On Day 22, the participant is no longer considered to have an acute illness. Should the participant continue to require ≥ 16 hours/day of ventilator support from day 22 to day 36, he or she shall be considered to meet the surrogate endpoint.

Statistical approach: The proportion surviving event-free to 14 months of age will be computed in the ITT population. Patients who terminate the study prior to reaching 14 months of age for any reason will be considered treatment failures (event).

As a comparator, in a natural history study of SMA Type 1 patients, [Finkel et al \(2014\)](#) estimated that only 25% of SMA Type 1 patients with 2 copies of *SMN2* would survive event-free to 13.6 months of age.

The observed proportion surviving in the current study will be compared to the natural history data [\(5\)](#) of the matching cohort using a two-sample Fisher’s exact test, along with the corresponding 95% confidence intervals.

If status at 14 months of age is coded using variable SURVIVE as 1 if patient survived to 14 months of age without requiring permanent ventilation, and 2 otherwise, then the SAS code to generate the endpoint analysis is:

```
proc format;  
value survive  
1= 'Yes'  
2= 'No'  
;  
Value grp  
1='AVXS'  
2='PNCR'  
;  
run;  
proc freq data=x order=data;  
table grp*survive / measures riskdiff;  
exact fisher / alpha=0.05;  
run;
```

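### SAP 6.3 makes entry to the primary analysis depend on unspecified baseline values that neither co-primary needs, in conflict with the ITT denominator of 5.2, 8.1.1 and 8.1.2

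*SAP*

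**What the plan says.** Section 6.3 of the SAP opens with a rule that takes each ITT patient into the "primary efficacy analysis for a given endpoint provided there are non-missing baseline values". It does not say which baseline values are meant. A little further on, the same section says: "For co-primary and co-secondary endpoints, missing values will be imputed as non-responsive".

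Section 5.2 builds the ITT population from symptoms, *SMN1* and *SMN2* genotype and treatment, the last being children "who receive an IV infusion of AVXS-101 at less than 180 days of age". It asks for no baseline measurement.

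The endpoint sections use that population. In Section 8.1.1, sitting "at 18 months of age study visit will be summarized for the ITT population". In Section 8.1.2: "The proportion surviving event-free to 14 months of age will be computed in the ITT population". Section 8.1.2 also counts anyone who leaves the study before 14 months of age as an event, whatever the reason.

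For the sitting items, Section 8.1.1 adds: "These milestones will also be assessed at the 18 months of age visit, regardless of previous attainment". It also requires a physical therapist to assess baseline milestones, including sitting, at Screening.

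**The concern.** The first sentence of Section 6.3 takes patients who are already in the ITT set and adds a further entry condition. Neither co-primary endpoint contains a change from baseline or depends on a baseline state, so a missing baseline value is no reason to leave a treated child out.

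The condition also pulls against the rules around it. A child whose outcome is missing stays in the denominator as a failure. A child whose outcome was observed to be a failure, but whose baseline value is missing, could be removed. In an open-label single-arm trial planned on about 15 ITT patients, each child is about 7 percentage points of the denominator (1/15 = 6.7%). Because the values are not named, the choice of which ones count is left open until outcomes may be known.

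At stake are the size of both co-primary estimates and, for survival, possibly the test result. Under the testing order in Section 8.4, a significant survival result also opens the co-secondary tests.

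**Working it through.** **1. Does either co-primary need a baseline value?**

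| Endpoint | Definition | Baseline term? |
|---|---|---|
| Sitting (8.1.1) | Video-confirmed status at the 18-month visit | None, but a screening milestone assessment exists |
| Event-free survival (6.2.4.1, 8.1.2) | Death, tracheostomy or permanent ventilation up to 14 months | None |
| Independence of ventilatory support (8.2.2) | No daily support at 18 months | None |
| Ability to thrive (4.1.2, 8.2.1) | Status at 18 months among children not requiring parenteral nutrition at baseline | Yes, by definition |

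Only ability to thrive needs one.

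**2. The plan's own power figures (Section 3.7).** The inputs are 15 patients less 30%, that is 15 × 0.7 = 10.5, so n = 10 or 11; sitting null 0.1%, alternative 30% to 40%, one-sided alpha 0.025; survival 80% versus 25% with 23 controls (Section 5.5), two-sided Fisher test at 0.05.

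- Sitting: with n = 10, P(at least 1 sitter | 0.1%) = 1 − 0.999^10 = 0.00996, which is below 0.025, so one sitter rejects the null. Power = 1 − (1 − p)^n. For n = 10 this is 1 − 0.7^10 = 97.2% and 1 − 0.6^10 = 99.4%. For n = 11 it is 98.0% and 99.6%. The stated >90% reproduces.
- Survival: summing the binomial probabilities of all outcome pairs with Fisher p ≤ 0.05 gives 82.4% (n = 10) and 84.6% (n = 11). The stated >80% reproduces.
- With all 15 patients: sitting 1 − 0.7^15 = 99.5% to 1 − 0.6^15 = 99.95%, exact alpha 1 − 0.999^15 = 0.0149; survival 92.9%. A full denominator costs no power.

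**3. Effect on sitting.** Assume 6 sitters among 15, the 40% rate in Section 3.7, and k children without a baseline value, all non-sitters. The lower limit is the exact one-sided 97.5% limit, the 0.025 quantile of Beta(x, n − x + 1).

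| k | Sitters/n | Rate | Lower limit |
|---|---|---|---|
| 0 | 6/15 | 40.0% | 16.3% |
| 1 | 6/14 | 42.9% | 17.7% |
| 2 | 6/13 | 46.2% | 19.2% |
| 3 | 6/12 | 50.0% | 21.1% |

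One sitter rejects the null at each of these sample sizes, so the test conclusion is the same in every row.

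**4. Effect on survival, if the clause is applied to it.** Section 5.5 gives 17 events among 23 controls by 13.6 months, so 23 − 17 = 6 event-free. Two-sided Fisher p against 6/23, dropping k children with events:

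| Event-free | k = 0 (n = 15) | k = 1 (n = 14) | k = 2 (n = 13) | k = 3 (n = 12) |
|---|---|---|---|---|
| 7 | 0.296 | 0.171 | 0.150 | 0.079 |
| 8 | 0.168 | 0.085 | 0.073 | 0.031 |
| 9 | 0.0486 | 0.038 | 0.017 | 0.011 |
| 12 | 0.0023 | 0.0006 | 0.0003 | <0.0001 |

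Nine or more of 15 is significant without any exclusion, and seven or fewer is not significant with up to three. The conclusion changes only at 8/15 with exactly three failures dropped. At the planned 80% survival, P(8 of 15) = 6435 × 0.8^8 × 0.2^7 ≈ 1.4%, before requiring that three of the seven failures, and no one else, lack a baseline value.

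**The case against.** The strongest reply rests on the words limiting the rule to a given endpoint. Read naturally, they mean that endpoint's own baseline where it has one. Event-free survival has none, so the clause would be empty there, and Section 8.1.2 on its own terms keeps every ITT patient and counts early leavers as events. This is a fair reading and it stands as a possibility, but the SAP does not state it. Section 6.2.4.1 does refer to ventilatory use at baseline, so a survival-related baseline is not inconceivable. For sitting the reply does not work, because the screening milestone assessment is exactly such a baseline.

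The second reply is that missing baselines will be rare. The relevant assessments are scheduled at Screening, CHOP-INTEND is repeated on Day -1 with a Day 1 fallback, and Section 6.2.1 accepts the last non-missing value before infusion. This also stands. The SAP gives no expected rate, so the zero to three used above is an assumption. Gaps are still possible: Section 4.2.1 sets the CHOP-INTEND total to missing if any item could not be tested.

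A reader might infer that the sickest infants are the ones without baseline data, and hence that the plan inflates both co-primary rates. The SAP contains nothing that links a missing baseline to prognosis, and missingness of pre-dose data is settled before any outcome. The direction of bias in the tables is therefore an assumption, not a finding.

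**Conclusion.** The concern holds as a conflict of stated rules. Followed as written, Section 6.3 can remove a treated child from a denominator that Sections 5.2, 8.1.1 and 8.1.2 define without that condition, while the neighbouring rule keeps children with missing outcomes as failures. This is clear for sitting. For survival it depends on a reading that the SAP leaves open.

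The likely effect is small. For sitting, mainly the estimate and its confidence limit move. For survival, the only reversal within zero to three excluded failures is at 8/15 with three dropped (p = 0.168 to 0.031). These sizes assume 15 ITT patients, that every excluded child is a failure, and that the 13.6-month control count stands in for 14 months. It would be wrong to conclude that the clause threatens the survival result at the planned effect: 12/15 gives p = 0.0023 with nobody excluded. The case for changing the text is that a primary denominator should not depend on how one loose sentence is read.

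**What to change.** In Section 6.3, delete the baseline proviso for functional independent sitting, event-free survival and independence of ventilatory support, and state that the denominator for each is every patient who meets Section 5.2.

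Keep a baseline condition where the quantity needs it: change-from-baseline summaries such as CHOP-INTEND and laboratory values, and ability to thrive. The last must not be given the full Section 5.2 denominator, because Sections 4.1.2 and 8.2.1 define it only among children not requiring parenteral nutrition at baseline.

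The cost is a short edit to one SAP section, with no new data, no change in sample size and no loss of power. If some baseline values are missing, the observed rates may be slightly less favourable. If none are, nothing changes.

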6.2.2. Definition of Study Days (Days Relative to the Gene Therapy Infusion)

Study Days are calculated for each time point in the treatment period relative to the gene therapy infusion of study drug. Study Days are negative values when the time point of interest is prior to the study drug infusion day. Study Days are positive values when the time point of interest is after the first study drug dose day. Study Day 1 is the day of the infusion of the gene therapy study drug.

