7.4. Prior and Concomitant Medications

Prior and concomitant medications will be summarized by overall. A prior medication is defined as any medication taken prior to the date of the gene therapy infusion of study drug. A concomitant medication is defined as any medication that started prior to the date of the infusion of study drug and continued to be taken after the infusion of study drug or any medication that started on or after the date of the infusion of study drug. The number and percentage of patients taking prior or concomitant medications will be summarized by generic drug name based on the WHO Drug Dictionary.

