10.3. Adverse Events / Adverse Drug Reactions

10.3.1. Treatment-Emergent Adverse Events

Adverse events will be coded using the Medical Dictionary for Regulatory Activities (MedDRA). Treatment-emergent adverse events are defined as any event that begins or worsens in severity after initiation of study drug through the last study visit. If an incomplete onset date was collected for an adverse event, the event will be assumed to be treatment-emergent, unless there is other evidence that confirms that the event was not treatment-emergent (e.g., the event end date was prior to the study drug start date).

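### Section 6.3, Tables 2 and 3: some partial start dates are imputed to the dose date although the recorded year, or the record's pre-dose status, rules that date out

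*SAP*

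**What the plan says.** Section 6.3 gives one table for pre-dose data (Table 2) and one for post-dose data (Table 3). Each has three rows, according to which part of the date is missing.

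- **Table 3, start dates.** For "Missing month and day, but the year is present" and for "Missing month, but year and day are present" the imputed start is the date of dose, with no condition on the year. For a missing day alone it is "First day of that month or dose date if the year and month are the same as the year and month of dose date".
- **Table 2, start dates.** With only the year known, the start is "January 1 of that year or dose date if the year is the same as the year of dose date". With only the day missing, the wording is the same as in the missing-day row of Table 3.
- **Table 2, stop dates.** A year-only stop becomes 31 December of that year, and a stop with a missing day becomes the last day of that month.

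Three other sections bear on the result.

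- Section 6.2.2: "Study Day 1 is the day of the infusion of the gene therapy study drug".
- Section 7.4: "A prior medication is defined as any medication taken prior to the date of the gene therapy infusion of study drug". Concomitant medication includes "any medication that started on or after the date of the infusion of study drug".
- Section 10.3.1: "If an incomplete onset date was collected for an adverse event, the event will be assumed to be treatment-emergent", unless other evidence shows that it was not.

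**The concern.** An imputed date should not contradict what was recorded. Two of the three start rules in Table 3 replace a known year, or a known year and day, with the dose date even when the known year is later than the dose year. The missing-day row avoids this, so the table is inconsistent with itself.

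Table 2 has a different fault. It keeps the known year or month, but it places a record that belongs to the pre-dose period on the dose date.

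At stake are the onset day and duration of partial-date records, any exposure total built from them, and the division of medications into prior and concomitant.

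**Working it through.** The SAP gives no figure to reproduce. The check applies the rules literally to worked dates. All dosing, birth and record dates below are illustrative assumptions; the SAP gives none.

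**1. Can a start fall in a later calendar year than dosing?** Inputs: dosing below 180 days of age (Section 3.7) and a final visit at 540 to 554 days of age (Section 3.5 and Table 4). Last study day = age at final visit − age at dosing + 1.

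- Shortest: 540 − 179 + 1 = 362.
- Longest: 554 − 1 + 1 = 554.

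A patient dosed on 1 January at 179 days of age and seen at 540 days finishes on 28 December, so a few patients could stay within one year. With dosing dates spread evenly over the year and over ages 1 to 179 days, and a final visit at 540 days, more than 99.9% of combinations cross into a later year.

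**2. Table 3, year only.** The recorded year is 2019 and dosing is in 2018. The earliest date that fits is 1 January 2019. Study Day = date − dose date + 1.

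| Assumed dose date | Start under Table 3 | Earliest possible start | Minimum error |
|---|---|---|---|
| 15 Jan 2018 | Day 1 | Day 352 | 351 days |
| 15 Apr 2018 | Day 1 | Day 262 | 261 days |
| 15 Jun 2018 | Day 1 | Day 201 | 200 days |
| 15 Sep 2018 | Day 1 | Day 109 | 108 days |
| 15 Dec 2018 | Day 1 | Day 18 | 17 days |

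**3. Table 3, month missing.** The record shows day 20 and year 2019, with dosing on 15 June 2018. The earliest date that fits is 20 January 2019, which is Study Day 220. The rule gives Study Day 1.

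**4. Table 2, year only, in the dose year.** Dosing is on 15 June 2018. A medication has a start year of 2018 and a recorded stop of 1 June 2018. The imputed start is 15 June 2018, after its own stop. Duration = 1 June − 15 June + 1 = −13 days. If the stop also has only the year, the record runs from 15 June to 31 December 2018, so a pre-dose course becomes wholly post-dose.

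**5. Table 2, the 1 January branch.** This branch applies only when the known year is before the dose year. Age at dosing is the date difference plus 1 (Section 7.2), so birth is at most 179 − 1 = 178 days before dosing. Even with dosing on 1 January, birth is no earlier than 7 July of the previous year. 1 January of that year is at least 187 days before birth. For any postnatal record, the year-only row of Table 2 therefore gives a start either before birth or on the dose date.

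**6. Effect on medication class.** Under Section 7.4, a medication started before infusion and continued after it is both prior and concomitant. If its start is imputed to the dose date and class is derived from that date, it stays concomitant but drops out of the prior summary. Table 3 cannot cause this, because a post-dose start moved to the dose date remains concomitant.

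**The case against.** The strongest reply is that little depends on these dates.

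- Section 10.3.1 already treats incomplete onsets as treatment-emergent, and a dose-date onset gives the same status.
- The adverse event tables in Section 10.3.2 count patients and events by class, term, grade and relationship. None is by onset day.
- The text just above Table 2 says that missing safety endpoint values are not imputed, so it is unclear whether adverse event onsets go through Table 3 at all. The SAP does not name the datasets that the tables serve.
- Section 7.4 defines prior by use before infusion, not by imputed start. A recorded pre-dose stop would still show prior use.
- A start imputed before birth is implausible, but it still precedes dosing and cannot change class.
- With frequent visits, dates lacking a month should be uncommon.

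All of this stands, and it limits the point. Three stronger readings are tempting and are not supported. A reader might infer that late events will be presented as acute infusion reactions, but no planned adverse event table shows time since infusion. A reader might infer that prior medications become concomitant only, but that requires class to be derived from the imputed start, which Section 7.4 does not say. A reader might infer that both tables discard known date parts, but only Table 3 does; Table 2 overrides pre-dose status.

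The reply does not remove the fault itself. Table 3 as written gives dates that the record rules out, and Table 2 gives dates outside the period it covers.

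**Conclusion.** The point holds as a minor, easily corrected error in stated rules. In Table 3, the year-only and missing-month rows date a start recorded in a later calendar year to Study Day 1, an error of at least 17 to 351 days in the worked examples. In Table 2, a start in the dose year or dose month lands on the dose date. That contradicts pre-dose status, can follow the recorded stop, and can cost a medication its prior class if class is taken from the imputed start.

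The effect is confined to onset day, duration or exposure, and prior or concomitant class, for partial-date records only. Use of the tables for medications and adverse events is inferred from their start and stop columns. The prednisolone day count and cumulative dose in Section 7.4.1 would be affected only if these tables feed them, which the SAP does not say. Treatment-emergent status, adverse event incidence and the efficacy tests are not shown to depend on the tables.

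**What to change.** Rewrite the two tables and name the datasets to which they apply.

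- **Post-dose start:** use the later of the dose date and the first day consistent with the known date parts. Where the month alone is missing and the year is the dose year, take the first date on or after dosing that keeps the recorded day.
- **Pre-dose start:** use the first day consistent with the known parts, not before birth, before dosing, and not after the recorded stop.
- **Pre-dose stop:** where the record is known to have ended before dosing, limit the imputed stop to before the dose date.
- **Section 7.4:** state whether prior and concomitant class is set from recorded pre-dose or post-dose status or from imputed dates.

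In the worked cases, the year-only start in 2019 becomes 1 January 2019. The pre-dose medication stopped on 1 June 2018 starts on the later of 1 January 2018 and the date of birth, provided that this is no later than the stop.

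The cost is an edit to two short tables and the matching date-imputation code. No new data or clinical decision is needed.
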